4.6. Setting

This study will take place in Ottawa and will involve personnel from the Centre for Health Innovation and The Ottawa Hospital & Ottawa Hospital Research Institute. Day-to-day study activities, including screening & recruitment, outcome collection & follow-up, and product dispensing & tracking, will be managed by study staff at the CHI under the supervision of the principal investigator. The principal investigator will communicate regularly with the qualified investigator and other members of the research team to ensure proper trial conduct. Study interventions will be taken at home by study participants.

5. Sample Size Determination and Power Calculation

With respect to the primary outcome of participant-reported overall health, power calculations were conducted based on between-group differences at a single time point (21 days) and Cohen's guideline for a small effect size of 0.3. A sample size of 176 (88 per arm) provides 80% power to detect a difference at an α of 0.05. To account for an approximate 10-15% lost to follow-up we will enrol 200 participants (100 per arm).

6. Data Collection, Analysis, and Management

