3.1. Study Design

This study is a double-blind, placebo-controlled, phase III randomized controlled trial powered to detect meaningful differences in the overall health and symptom severity of people with COVID-19 between the treatment and control arms. Eligible participants will be randomly assigned, using a web randomization system, in a ratio of 1:1 to one of the following groups: (1) nutrient therapy with vitamin D, vitamin C, vitamin K2, and zinc or (2) placebo. Total trial duration will be 12 weeks. Nutrients or placebo will be given for a period of 21 days following enrolment and randomization. The length of the intervention period (21 days) encompasses the most common period within which recovery occurs. The median duration of time to symptom resolution is 4-8 days from testing and yet a substantial number of people (26-47%) do not return to their usual state of health within 14-21 days.³³ Available guideline recommendations support a prolonged follow up period in order to assess patients experiencing ongoing symptomatic COVID-19 (signs and symptoms for 4-12 weeks) and those with post-COVID-19 syndrome (signs and symptoms >12 weeks).³⁴

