4.5. Randomization, Blinding, and Control

Participants will be randomized in a 1:1 ratio using a web-based tool provided and maintained by an independent statistician at the Ottawa Methods Centre. Randomization will be based on mixed block sizes of 4 and 6 to ensure adequate balance at all stages of recruitment.

All products will have an equivalent placebo such that each product and pill bottle are both indistinguishable from the treatment, except for the lot number, which will allow Vitazan to distinguish between treatment and placebo. Study participants and research staff will remain blinded for the duration of the study until recruitment is finished and all analyses are completed. The Data Safety and Monitoring Board (DSMB) may request that participants be unblinded if they are concerned about participant safety (e.g., due to the distribution of adverse events). In this case, the PI and QI will be notified of the unblinding and this will be documented and stored in the study binder.

Compliance to the study protocol will be participant-reported during the weekly calls by the research staff. Participants will be instructed to return all partially used and unused investigational products to the CHI or their local pharmacy for destruction. All efforts will be made to ensure participants start the study product as soon as possible after enrolment and randomization. Days from symptom onset to starting the study product will be monitored and compared between arms to ensure consistency.

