6.2. Data Analysis

6.2.1. Analysis Plan

6.2.1.1. Participant-Reported Overall Health & Health Status

The primary outcome analysis of participant-reported overall health will be conducted using an area under the curve approach comparing the mean difference between arms in the EQ-VAS over the 21-day intervention period. Scores will range from 0-2100 (i.e., 0-100 for 21 days) for each participant.

Health status will be measured using the crosswalk value approach. Each level from each domain of the EQ-5D-5L is aggregated to form a number defining a unique health state, with 11111 (i.e., a “1” in all domains) representing the best possible health status and 55555 (i.e., a “5” in all domains) representing the worst possible health status. Raw values will be converted to an index value out of 1. Differences in mean index values will be compared between arms at various time points over the 12-week study period. Index values will be calculated using the United States crosswalk value set provided by the EuroQol group.^{65,66}

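### The 80% power in Section 5 is stated for a day-21 EQ-VAS comparison that the plan never runs, it does not hold for that comparison either, and the power claimed for symptom severity has no calculation

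*Combined protocol and SAP*

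**What the plan says.** Section 5, on the primary outcome, states that "power calculations were conducted based on between-group differences at a single time point (21 days") and uses "Cohen's guideline for a small effect size of 0.3". It then says: "A sample size of 176 (88 per arm) provides 80% power", at an α of 0.05. Sidedness, an SD and a difference in EQ-VAS points are not given.

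Section 6.2.1.1 defines a different quantity: "The primary outcome analysis of participant-reported overall health will be conducted using an area under the curve approach", with a range of 0 to 2100, which is the sum of 21 daily scores. Section 6.2.2 assigns an unadjusted t-test to it. The comparisons at several time points in Section 6.2.1.1 concern the EQ-5D-5L index, which is a separate measure.

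Section 3.1 describes the trial as "powered to detect meaningful differences in the overall health and symptom severity of people with COVID-19". Section 2.1.2 lists symptom severity as a secondary objective, and Section 5 does not mention it.

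**The concern.** A power statement should belong to the test that decides the trial. Here it is attached to one day's score, while the deciding test uses 21 days. A 21-day sum has its own SD and its own treatment effect. An effect of 0.3 SD on day 21 becomes an AUC effect only through a day-to-day correlation and an assumed course of the effect over time, and Section 5 gives neither.

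Two things are at stake. A reader will take 80% as the chance of detecting the stated effect in the primary analysis, and that figure is unsupported. A reader will also take a null symptom-severity result as coming from a comparison with adequate power, which the documents do not show. Correcting the day-21 arithmetic alone would leave the statement on the wrong endpoint. Relabelling the endpoint alone would leave the arithmetic wrong.

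**Working it through.** **Inputs from the documents.** Standardised effect 0.3, α 0.05, 88 per arm, 80% power (Section 5); 1:1 allocation (Section 4.5); AUC over 21 daily scores (Section 6.2.1.1); unadjusted t-test (Section 6.2.2). Two-sided testing is assumed.

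**Step 1: the plan's own figure.** Power of a two-sample t-test (noncentral t) with d = 0.3:
- 88 per arm, two-sided 5%: 50.8% (normal approximation 51.2%).
- 88 per arm, one-sided 5%: 63%.
- Needed for 80%, two-sided: 175.4, so 176 per arm (normal approximation 175).

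The stated 80% is not reproduced. The stated total of 176 equals the per-arm requirement, but the documents do not say how it arose.

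**Step 2: what 88 per arm can detect.** Solving for 80% power at two-sided 5% gives d = 0.42. This holds for any t-test with 88 per arm, including the AUC test, when d is expressed in SDs of the variable tested.

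**Step 3: from a daily effect to an AUC effect.** Dividing the AUC by 21 gives the 21-day mean, and the standardised effect is unchanged. Assume equal SDs on all days and exchangeable correlation ρ. In daily-SD units:

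SD of the 21-day mean = √((1 + 20ρ)/21) = 0.655, 0.787, 0.900 for ρ = 0.4, 0.6, 0.8.

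AUC effect size = mean daily effect ÷ that SD.

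Mean daily effect, for three assumed courses that all equal 0.3 SD on day 21:
- constant: 0.3
- falling linearly from 0.45 to 0.3: (0.45 + 0.30)/2 = 0.375
- growing linearly to 0.3: 0.3 × 11/21 = 0.157

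| Course of effect | AUC effect size at ρ = 0.4 / 0.6 / 0.8 | Power, 88 per arm, two-sided 5% |
|---|---|---|
| Constant | 0.46 / 0.38 / 0.33 | 86% / 71% / 59% |
| Falling | 0.57 / 0.48 / 0.42 | 97% / 88% / 79% |
| Growing | 0.24 / 0.20 / 0.17 | 35% / 26% / 21% |

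The right baseline for this table is the 51% of Step 1, not the stated 80%. Under a constant effect and equal SDs, the SD of the mean cannot exceed one daily SD, so AUC power cannot fall below 51%. It falls below only when the average daily effect is sufficiently smaller than the day-21 effect.

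**Step 4: symptom severity.** Section 6.2.1.2 gives a score range and an AUC approach. No section gives an effect size, an SD or a power for it, so nothing can be computed.

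**The case against.** The best defence is that 0.3 is standardised, so the same arithmetic serves a t-test on the AUC, and that Section 5 opens by naming the primary outcome. That stands if 0.3 is declared as the AUC effect. Section 5 instead ties it to one time point, and even when declared for the AUC it gives about 51%, not 80%.

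A second defence is that sizing on a single day is a common simplification and is conservative for a steady or early effect. This is partly right: the constant and falling rows all exceed 51%. Section 3.1 puts median symptom resolution at 4–8 days from testing, which is compatible with an early effect. But Section 5 neither claims conservatism nor gives the inputs to show it.

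Three stronger readings are tempting and are not supported:
- *Moving to the AUC costs power.* The growing-effect row alone suggests this. It rests on an assumed shape, and most of the apparent shortfall in the constant-effect cases disappears once 51% replaces 80% as the baseline.
- *Nobody can know what the primary test detects.* Step 2 gives it, in SDs of the AUC. What is missing is the translation into EQ-VAS points.
- *The loss allowance is a further error.* The plan says "To account for an approximate 10-15% lost to follow-up we will enrol 200 participants (100 per arm"). Since 176/200 = 0.88, enrolling 200 covers 12% loss, inside a range labelled approximate. At 15% loss 170 remain, and power at d = 0.425 falls only from about 80% to 79%.

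The symptom-severity phrase is indeed one clause in a design overview. It changes no test, but it asserts a property that is not shown.

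**Conclusion.** The point holds. The 80% in Section 5 is not the power of the primary AUC test, and it is not the power of the day-21 comparison either, which is about 51% at two-sided 5%. The documents do not fix the AUC power. Under the assumptions in the working (equal daily SDs, exchangeable correlation 0.4–0.8, three illustrative courses) it runs from 21% to 97%, on both sides of 51%. Equal daily SDs is a convenience and may not hold on a 0–100 scale in recovering participants. The power claim for symptom severity has no support in the plan. The validity of the planned t-test is not affected: the fault is in what is said about its power.

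**What to change.** Restate Section 5 for the t-test on the 21-day AUC at the planned 88 per arm, and state the sidedness. Either form would do:
- the effect detectable with 80% power, about 0.42 SD of the AUC, also expressed as a difference in mean EQ-VAS points (AUC/21) with the assumed SD; or
- the power at a declared AUC effect, about 51% if 0.3 is the declared value.

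If the effect is carried over from a single day, state the assumed daily SD, day-to-day correlation and course of effect, with a short sensitivity table that includes an early-effect case.

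In Section 3.1, delete the reference to symptom severity or add its calculation. The loss allowance needs no separate correction.

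The cost is a rewrite of one short section and one phrase. These changes need no extra participants. The drawback is a less favourable stated figure.

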4.2.3. Adherence to the Protocol

4.2.3.1. Protocol Amendments

All amendments to this protocol will be reviewed by both REBs and submitted to the NNHPD and the TPD as either a notification or Clinical Trial Application Amendment (CTA-A). Both the principal investigator and qualified investigator will sign the approved protocol prior to implementation, and each investigator and member of the research team will be adequately trained prior to carrying out and study-specific tasks after the approval of the amendment.

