6.2.2. Statistical Methods

All analyses will follow an intention to treat approach. Continuous and quasi-continuous variables (participant-reported health & health status, primary & secondary severity analyses, and length of stay) will be compared between arms using unadjusted t-tests. Dichotomous outcomes (incidence of severe symptoms, delayed return to usual health, hospitalizations and deaths) will be compared between arms using Chi-square tests or Fisher's exact tests where appropriate. Time to symptom resolution will be displayed graphically with Kaplan-Meier curves and differences between arms will be compared with a log-rank test.

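### Section 5 claims 80% power for an effect of 0.3 with 88 per arm; those inputs give 50.8% two-sided (63.2% one-sided), and two-sided 80% needs 176 per arm, not 176 in total

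*Combined protocol and SAP*

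**What the plan says.** Section 5 bases the calculation for participant-reported overall health on a difference between groups at one time point, day 21, with an effect size of 0.3 described as small on Cohen's guideline. It then states: "A sample size of 176 (88 per arm) provides 80% power to detect a difference at an α of 0.05". Enrolment is set at 200 (100 per arm) to allow for roughly 10-15% loss. Neither the sidedness of the test nor a standard deviation is given.

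The other inputs are elsewhere in the same document. Section 4.5: "Participants will be randomized in a 1:1 ratio". Section 6.2.2 says that continuous outcomes, including the primary one, "will be compared between arms using unadjusted t-tests". Section 6.2.1.1 defines the primary analysis as an "area under the curve approach comparing the mean difference between arms in the EQ-VAS over the 21-day intervention period", which is not the single-day comparison used for power. Section 3.1 describes the trial as "powered to detect meaningful differences in the overall health and symptom severity of people with COVID-19".

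**The concern.** A two-sided two-sample comparison at a standardised difference of 0.3 is usually known to need about 175 per arm for 80% power. Section 5 gives almost exactly that number as the total for both arms.

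This paragraph is the only sample size justification in the plan. If it is wrong, the ethics boards and regulators have been given a power that its own inputs do not produce. Reading of the result is also affected. Section 10 expects a negative finding to help keep patients from paying for an ineffective therapy, but a null result from a trial with about an even chance of detecting 0.3 SD cannot support that inference for an effect of that size. Type I error and the validity of the effect estimate are not affected.

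**Working it through.** **Inputs.** Effect size 0.3, 88 per arm, α = 0.05, claimed power 80%, 10-15% loss, 200 enrolled (Section 5); 1:1 allocation (Section 4.5); unadjusted t-test (Section 6.2.2). The effect size is read as d = (mean difference)/SD, the natural reading for a t-test. Both sidedness options are computed.

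**Attempt to reproduce 80%.** With n per arm, the t statistic has 2n − 2 degrees of freedom and noncentrality d·√(n/2).

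- For n = 88: 0.3 × √44 = 1.990, with 174 degrees of freedom.
- Two-sided critical value 1.974: power 50.8%.
- One-sided critical value 1.654: power 63.2%.

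The normal approximation gives 51.2% and 63.5%. A simulation of 60,000 two-sided trials gave 50.7%. The stated 80% is not reproduced.

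**Power at d = 0.3 for the sample sizes that the plan implies (noncentral t).**

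| Evaluable per arm | Two-sided | One-sided |
|---|---|---|
| 85 (15% loss from 100) | 49.4% | 61.9% |
| 88 (as stated) | 50.8% | 63.2% |
| 100 (no loss) | 56.0% | 68.1% |

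On loss: 200 × 0.88 = 176, so the planned 176 survives up to 12% loss. At the stated upper limit, 200 × 0.85 = 170, or 85 per arm.

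**Sample size needed for 80% at d = 0.3.** Normal formula, two-sided: n per arm = 2(1.960 + 0.842)²/0.3² = 2 × 7.849/0.09 = 174.4. The noncentral t gives 175.4, so 176 per arm (power 80.1%), 352 in total. One-sided it gives 138.1, so 139 per arm.

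**Difference detectable with 80% power at 88 per arm.** 0.425 SD two-sided; 0.376 SD one-sided.

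**Other readings tried.**

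- A one-sample or paired t-test with n = 88 gives 79.5% two-sided, but the plan compares two separate arms.
- Cohen's f = 0.3 needs about 90 in total for 80%, and a correlation of 0.3 about 85 in total; neither leads to 176.
- Two-sided α of 0.10 or 0.20 gives 63.5% or 76.1%.
- Baseline adjustment would need a correlation of about √(1 − 88/174.4) = 0.70, but the tests are unadjusted and Table 1 schedules no baseline EQ-VAS.

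**Possible cause.** Omitting the factor 2 from the normal formula gives 87.2, rounded up to 88. Reading the per-arm 176 as a total gives the same figure. The documents do not show which slip, if either, occurred.

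**The AUC.** If 0.3 is itself the standardised effect on the 21-day AUC, the figures above apply to the primary test. If it is a day-21 effect, the answer depends on the between-day correlation r and the time course of the effect, and neither is given. The following is illustrative only. It assumes 21 daily values, equal daily SD, equal correlation, 88 per arm and a two-sided test. The standardised AUC effect is then (mean daily effect)/√((1 + 20r)/21).

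| Assumed daily effect (SD) | r = 0.4 | r = 0.5 | r = 0.8 |
|---|---|---|---|
| Constant 0.3 | 86% | 78% | 59% |
| Rising linearly to 0.3 at day 21 | 35% | 30% | 21% |
| Falling linearly from 0.5 to 0.3 | 98% | 95% | 84% |

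**The case against.** The strongest counter-argument is that the primary test uses 21 daily scores, and averaging over days can raise power above that of a single day. An effect that is largest early and shrinks by day 21 is plausible, since Section 3.1 cites median symptom resolution of 4-8 days from testing. In the last row of the illustration, power for the AUC exceeds 80% throughout. This stands as a limit on scope: the trial's real power could be above or below 80%. It does not rescue Section 5, which says that its calculation used one time point and offers no correlation or time course. Even with a constant daily effect of 0.3, 80% requires r of about 0.47 or lower.

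A second point is that 0.3 is not explicitly labelled a standardised mean difference. As Cohen's f (d = 0.6) or as a correlation (d about 0.63), 88 per arm would give about 98%. The size and direction of the error therefore depend on reading 0.3 as d, but no reading tried gives both 80% and 176 under the stated two-arm design.

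The remaining objections are fair but minor. The 15% loss case costs only 1.4 percentage points (50.8% to 49.4%). The symptom-severity wording in Section 3.1 is a question of coverage, not arithmetic.

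**Conclusion.** The power statement in Section 5 is wrong as written. With d = 0.3, α = 0.05, 88 per arm and an unadjusted two-sample t-test, power is 50.8% two-sided or 63.2% one-sided. The chance of missing the target difference is 49.2% or 36.8%, against the 20% implied. Two-sided 80% power requires twice the stated number.

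The conclusion rests on reading 0.3 as a standardised mean difference and applies to the calculation as Section 5 describes it. Power for the 21-day AUC is undetermined unless 0.3 is the effect on the AUC. Section 3.1 repeats the claim of adequate power for overall health and adds symptom severity, for which Section 5 gives no calculation.

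**What to change.** Restate Section 5 along these lines: with 88 evaluable participants per arm and two-sided α of 0.05, an unadjusted t-test on the 21-day EQ-VAS AUC has 80% power for a standardised AUC difference of about 0.425, and power at 0.3 is about 51%. If a one-sided test was intended, say so and give 0.376 and 63%. If 0.3 was meant as a day-21 effect, state the between-day correlation and effect time course used to carry it to the AUC. Bring Section 3.1 into line, and either support or remove its claim to be powered for symptom severity.

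This correction changes wording only and needs no extra enrolment. Under Section 4.2.3.1 it goes to both research ethics boards and to the two Health Canada directorates. The cost is a less favourable stated figure, which may prompt questions about whether 0.425 SD is a plausible and meaningful target; the sponsor should be ready to justify it. Keeping 0.3 with two-sided 80% power on the single-time-point calculation would be a different decision: 352 evaluable, or 352/0.90 = 392 to 352/0.85 = 415 enrolled (rounded up).

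### Minor: enrolling 200 keeps the planned 176 only up to 12% loss to follow-up; at the 15% end of the stated range 170 (85 per arm) remain

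*Combined protocol and SAP*

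**What the plan says.** Section 5 (Sample Size Determination and Power Calculation) bases the calculation on a between-group comparison at day 21 and on Cohen's "guideline for a small effect size of 0.3". It continues: "A sample size of 176 (88 per arm) provides 80% power to detect a difference at an α of 0.05". The attrition sentence follows directly: "To account for an approximate 10-15% lost to follow-up we will enrol 200 participants (100 per arm".

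Section 5 does not say which rate in the 10-15% range produced 200, gives no inflation formula, does not state whether the test is one- or two-sided, and does not say by what time point the loss is counted.

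Section 4.5 sets the allocation: "Participants will be randomized in a 1:1 ratio". Section 6.2.2 specifies intention to treat and says that continuous outcomes, including the primary one, "will be compared between arms using unadjusted t-tests". Under sections 3.7 and 6.2.1.1 the primary outcome is built from daily EQ-VAS scores over the 21 days of treatment, while follow-up continues to week 12.

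**The concern.** A reader takes an attrition allowance to mean that the planned analysis size survives the loss it names. Here the two printed totals, 176 and 200, fix the tolerable loss at one value inside the named range, and that value is nearer its lower end. A trial that loses 13-15%, which lies within the plan's own expectation, could therefore finish with fewer than 176 in the primary analysis, and the protocol gives no sign of it.

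What is at stake is the accuracy of a figure that the plan relies on, more than the power of the trial. The sentence also takes 176 (88 per arm) as the size to protect. A corrected attrition statement should not repeat that target without saying what it delivers at the stated effect size.

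**Working it through.** **Inputs, all from section 5 except allocation (section 4.5) and test (section 6.2.2):** planned size 176 (88 per arm); enrolment 200 (100 per arm); loss about 10-15%; effect size 0.3 SD; alpha 0.05; stated power 80%; 1:1 allocation; unadjusted t-test. A two-sided test is my assumption. It affects the power figures but not the attrition arithmetic.

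**1. The loss rate that reproduces 200.** With enrolment = n/(1 - loss), 176/(1 - loss) = 200 gives loss = 1 - 176/200 = 12.0%.

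**2. The stated range.** Required enrolment is rounded up to equal arms.

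| Loss | Left from 200 | Enrolment needed to keep 176 |
|---|---|---|
| 10% | 200 x 0.90 = 180 (90 per arm) | 176/0.90 = 195.6, so 196 |
| 12% | 200 x 0.88 = 176 (88 per arm) | 176/0.88 = 200 |
| 12.5% (midpoint) | 200 x 0.875 = 175 | 176/0.875 = 201.1, so 202 |
| 15% | 200 x 0.85 = 170 (85 per arm) | 176/0.85 = 207.1, so 208 |

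The cruder formula n x (1 + loss) gives 176 x 1.10 = 193.6 (194) and 176 x 1.15 = 202.4 (203). Neither formula makes 200 sufficient at 15%.

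**3. Cost on the plan's own premise.** Power comes from the noncentral t distribution with noncentrality d x sqrt(n/2) and 2n - 2 degrees of freedom, where n is the number per arm. The effect that gives 80.0% power at 88 per arm is d = 0.4247. The documents do not state this value; it is solved from their 80% and 88 per arm. At 85 per arm the same effect gives 78.6%, a loss of about 1.4 percentage points.

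**4. Power at the stated effect size of 0.3.**

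| Per arm | Noncentrality | Two-sided power |
|---|---|---|
| 88 | 0.3 x sqrt(44) = 1.99 | 50.8% |
| 85 | 0.3 x sqrt(42.5) = 1.96 | 49.4% |

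A one-sided test would give 63.2% and 61.9%, also well short of 80%.

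**5. Detectable effect at 80% power.** The normal approximation is (1.960 + 0.842) x sqrt(2/n). It gives 0.422 SD at 88 per arm and 0.430 SD at 85 per arm. The t-test value at 88 is 0.425.

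**6. The base figure.** For d = 0.3, two-sided, 80% power, the normal formula 2 x (1.960 + 0.842)^2 / 0.3^2 gives 175 per arm after rounding up. The t-test gives 175.4, so 176 per arm. The printed 176 therefore matches a per-arm requirement and does not reproduce as a total. The documents do not show how it arose.

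**The case against.** The strongest reply is that the sentence is a planning statement. It says approximate and gives a range. That range implies enrolment of 196 to 208, and 200 lies inside it. At the midpoint, 12.5%, 200 leaves 175, one short of target. This stands in part: the 10-12% portion is covered, and the fault is that the sentence does not say where cover stops. But the word approximate qualifies the loss rate. It does not tell the reader that cover ends at 12%.

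A second reply is that loss to follow-up is not the same as loss from the primary analysis. Someone lost between day 21 and week 12 still has a complete primary outcome, and the analysis is by intention to treat. This stands. The figure of 170 assumes that the whole loss falls before day 21 is complete. No method for missing daily scores is given, so the documents do not settle the matter.

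A third reply is that the effect is negligible beside the base-figure problem in the same paragraph. The relative weight is right, and it is why the point is minor and should be handled with that correction. It does not make the attrition sentence accurate.

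Three stronger readings are tempting and not supported:
- **That the plan promises 176 at every rate up to 15%.** Section 5 makes no such promise. Keeping 176 is a fair inference for some rate in the range.
- **That the plan treats 13-15% loss as acceptable.** It gives an expected loss and sets neither a limit nor a retention target.
- **That the allowance fails across the whole range.** It fails only above 12%.

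**Conclusion.** The point holds as a minor inaccuracy. Enrolling 200 retains the planned 176 up to 12.0% loss. Above that, still within the stated range, the number falls below 176 and reaches 170 (85 per arm) at 15%. This rests on the loss occurring before the day-21 primary outcome is complete and on equal loss in the two arms.

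On the plan's premise of 80% power at 88 per arm, the worst case within the range is about 78.6%. A reader might infer that attrition is what threatens the trial's power. The numbers do not support that: at the stated effect size of 0.3, two-sided power is already about 51% at 88 per arm, and falls to about 49% at 85. Nor would enrolling 208 instead of 200 bring power at 0.3 to 80%, since it would only keep 88 per arm at 15% loss.

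**What to change.** Replace the attrition sentence in section 5 with one along these lines: *Enrolling 200 (100 per arm) retains 176 (88 per arm) with up to 12% loss before completion of the day-21 primary outcome; at 15% loss, 170 (85 per arm) remain. With a two-sided t-test at alpha 0.05, power at an effect size of 0.3 is about 51% with 88 per arm and 49% with 85 per arm; the effect detectable with 80% power is about 0.42 SD and 0.43 SD respectively.*

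This states the sidedness and the time point at which loss is counted, both now missing. If the sponsor intends a one-sided test, the power and detectable-effect figures must be recalculated.

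Make the change together with any correction of the base figure of 176. If that figure changes, derive the new enrolment from n/(1 - loss) and name the rate used.

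The cost is a short edit to section 5 and a slightly less favourable statement of attrition tolerance. No extra enrolment is asked for, and trial conduct and the analysis are unchanged.
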